3.8. Dosage and Administration of Study Treatment(s)

GSK2857916 will be administered intravenously over 60 minutes. Subjects enrolled in Schedule 1 will receive one dose every 3 weeks (21 days) for a maximum of 16 cycles (16 doses). Subjects enrolled in Schedule 2 will receive one dose per week for 3 consecutive weeks followed by 1 week rest (28 day cycle) for a maximum of 16 cycles (48 doses).

The maximum dose to be administered to subjects in this trial is 5 mg/kg.

Refer to Section 4 for details on preparation and handling, and administration instructions of GSK2857916.

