Serum (cytokines/chemokines)		X ¹⁹	X			X ¹⁹	At predose and EOI on D1 of each cycle	X	
Serum (anti-drug-antibodies)	X					X ²⁰	At the start of cycles 3 ²⁰ , 6 ²⁰ , 9 ²⁰ , 12 ²⁰ and 16 ²⁰	X	
Plasma-cfDNA	X							X	
Peripheral blood (flow for TBNK)	X ¹⁵					X ¹⁵	At the start of each cycle ¹⁵	X ¹⁵	
Serial Pharmacokinetics (blood)		X ²¹	X ²¹	X ²¹	X ²¹	X ²¹	C3D1 only ²¹	X ²²	
Urine PK	X ²³					X ²³	Day 1 of cycles 4 ²³ , 7 ²³ , 10 ²³ , 13 ²³ , 16 ²³		
Premedication if needed		X				X	At the start of each cycle		
GSK2857916 administration		X ²⁴				X ²⁴	X ²⁴		
Steroid eye drops		X ²⁵				X ²⁵	X ²⁵		
Adverse Events							Continuous		

Time and Events Table for Full Study (Cycle = 21 days)										
Study Assessments ¹	Screen ²	Day 1 C1	Day 2 C1	Day 8 C1	Day 15 C1	Day 1 C2	D1 of C3-C16	End of Study Treatment	3-Month Off-study Follow-up	
Concomitant Medications	X	Continuous								
Survival Status									X ²⁶	
Subsequent Treatment									X ²⁶	

- Assessments scheduled on days of dosing should be done prior to drug administration, unless otherwise specified. All other assessments can be ± 3 days of scheduled occurrence unless otherwise specified.
- All Screening assessments must be performed within 14 days prior to first dose unless otherwise specified. Informed Consent must be signed before any study-specific assessments are performed.
- Screening examination to include BCVA (best-corrected visual acuity), slit lamp examination (with special focus on cornea), intraocular pressure, and dilated fundoscopic examination may be performed within 21 days prior to first dose.
- On-study exams to include BCVA (best-corrected visual acuity) and slit lamp examination (with special focus on cornea); window for exams is up to 3 days prior to dosing.
- On initial (first infusion) dosing day, vital signs must be assessed at pre-dose (within 30 minutes prior to SOI), +10 minutes and +30 minutes (± 5 min) after SOI, EOI, and 1 hour post EOI. On subsequent dosing days, vital signs must be assessed at pre-dose (within 30 minutes prior to SOI), +30 minutes after SOI, and EOI. The Sentinel Subject must be observed for at least 24 hours post EOI. **On days where vital sign timepoints align with PK sampling timepoints, vital signs should be assessed prior to PK samples being drawn.**
- If completed within 72 hrs prior to the first dose, this assessment need not be repeated on Day 1 of Cycle 1. Refer to [Table 15](#) for comprehensive list of lab tests.

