19. Collect cytokines at predose (within 30 minutes prior to SOI) and EOI (± 5 min) (even when infusion is interrupted or halted) to assess allergic reaction)
20. All ADA samples will be collected prior to each infusion
21. PK samples to be taken (in all subjects) for both GSK2857916 and cys-mcMMAF measurement: C1D1 at pre-dose (within 30 minutes prior to SOI), 0.5 h after the start of the infusion (SOI) (± 5 min), at the end of infusion (EOI) just before EOI, 1 h after EOI, 3 h after EOI (± 5 min), 8 h after EOI (± 15 min), 24h after EOI (± 1 h) (Day 2); C1D8 1 sample; C1D15 1 sample; C2D1, at pre-dose (within 30 minutes prior to SOI) and at the EOI (just before EOI); C3D1 at pre-dose (within 30 minutes prior to SOI) and at the EOI (just before EOI).
22. Collect 1 PK sample at each subject's final visit.
23. Pre-specified amounts of urine will be collected for PK analysis from the 24 hour urine collection at Screening, C2D1, C4D1, C7D1, C10D1, C13D1, and C16D1. Refer to Section 7.4.2 for details.
24. Study drug administration ± 3 day window only
25. Prophylaxis with prednisolone phosphate 1% or dexamethasone 0.1% 1 drop QID x 4 days starting 1 day prior to treatment
26. Record subject's survival status and whether subsequent treatment for disease was given. Subject does not need to come in for visit.

Abbreviations:

ADA = Antibody Drug Antibody; ALP = alkaline phosphatase; BCVA = best corrected visual acuity; BNP = B-type natriuretic peptide; C1D1 = Cycle 1 Day 1, etc.; cfDNA = Circulating free DNA; CK = creatinine kinase; CRP = C-reactive protein; EM = extramedullary; EOI = End of Infusion; FLC = free light chain; PD = Pharmacodynamics; PK = Pharmacokinetics; QID = 4 times a day; SOI = start of infusion; SPEP = serum protein electrophoresis; UPEP = urine protein electrophoresis

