7.4.2. Urine Sample Collection for Pharmacokinetics

Urine samples of approximately 1 mL for pharmacokinetic (PK) analysis of cys-mcMMAF will be collected from the 24 hour urine collection sample as scheduled in the Dose Escalation Time and Events Tables (Section 7.1.1). The actual date and time of each urine sample collection as well as the urine volume collected will be recorded. In addition for qualitative analysis of any metabolite(s) approximately 20mL of control is required prior to dosing and a 400mL aliquot as described in the Time and Events Schedules (Section 7.1.1)

Details on PK urine sample collection, processing, storage and shipping procedures are provided in the Study Procedures Manual (SPM).

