In Part 2 of the study, plasma GSK2857916 concentration-time data together with data from part 1 will be analysed using a population approach. A nonlinear mixed effects model will be used to determine population pharmacokinetic parameters and identify relevant covariates (e.g., age, weight, or disease related covariates). PK parameters will be listed and summarized descriptively (mean, standard deviation, median, minimum, maximum, geometric mean, and the standard deviation, CV% and 95% confidence interval of log-transformed parameters) by dose cohort and schedule in Part 1 and Part 2. To assess the extent of accumulation following GSK2857916 repeat dosing, the observed accumulation ratio (R_o) for both GSK2857916 (intact and total) and cys-mcMMAF will be determined as C_{max} and C_{trough} at steady-state to C_{max} and C_{trough} after the first dose, respectively.

Raw urine Concentrations

Urine concentrations of cys-mcMMAF (part 1 only) will be listed and summarised by GSK2857916 dose, schedule and nominal time range. Plots may also be produced if deemed necessary.

Derived Urine Pharmacokinetic Parameters

If data permits, the following pharmacokinetic parameters will be determined for each GSK2857916 dose, each schedule and for each subject (Part 1 only):

Urinary recovery of unchanged cys-mcMMAF within the 24 h period collection ($A_e(0-24)$) will be calculated. It will be calculated as the product of the concentration in urine and the urine weight, thus assuming a urine density of 1 g/mL.

Fraction of total cys-mcMMAF dose excreted (F_e) in the 24-h interval will be estimated as $A_e(0-24)/(\text{cys-mcMMAF})\text{Dose}$, in the Schedule 1 only (i.e. every 3weeks).

Derived cys-mcMMAF urine pharmacokinetic parameters will be listed and summarised by GSK2857916 dose and schedule.

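### As scheduled, no 24-hour urine collection covers the first 24 hours after a dose, so the parameters called Ae(0-24) and Fe would be end-of-interval amounts under the wrong name

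*Protocol*

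**What the plan says.** Section 13.7.3.1, under the derived urine parameters, defines Ae(0-24) as "Urinary recovery of unchanged cys-mcMMAF within the 24 h period collection", calculated as urine concentration times urine weight. It is planned for each dose, schedule and subject in Part 1 where the data allow. Fe "in the 24-h interval will be estimated as" Ae(0-24) over the cys-mcMMAF dose, on Schedule 1 only. Both are to be summarised by dose and schedule; cycle is not mentioned.

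Section 7.4.2 says that the urine for this assay "will be collected from the 24 hour urine collection sample as scheduled in the Dose Escalation Time and Events Tables". For Schedule 1, footnote 23 of the table in Section 7.1.1.1 takes the aliquots "from the 24 hour urine collection at Screening, C2D1, C4D1, C7D1, C10D1, C13D1, and C16D1". Footnote 24 of the weekly table in Section 7.1.1.2 lists the same visits. Neither table has urine PK on C1D1 or C1D2.

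Footnote 1 of both tables sets the timing rule: "Assessments scheduled on days of dosing should be done prior to drug administration, unless otherwise specified".

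**The concern.** A parameter written Ae(0-24) and divided by a dose will be read as the amount and fraction excreted in the 24 h after that dose. The schedule, followed literally, supplies urine from the 24 h before the next dose. The result would be an end-of-interval amount presented as an early recovery. In later cycles it would also contain drug from several earlier doses while being divided by one.

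The PK of cys-mcMMAF is part of a secondary objective, and Section 1.2.3.3 says that renal excretion could not be assessed quantitatively in the rat. Ae and Fe are the only quantitative measures of renal excretion that the protocol plans. A low Fe that is really an end-of-interval figure could be taken to mean that little is excreted in urine. Because the summary is not split by cycle, values from Cycle 2 and Cycle 16 could also be pooled.

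**Working it through.** The protocol gives no figure on this point to reproduce. The check sets the schedule against the definition, then uses interval arithmetic and an illustration.

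**1. Does an exception to the pre-dose rule exist?** In the Section 7.1.1.1 table, the footnotes for vital signs (5), ECG (11), sBCMA (18), cytokines (19) and blood PK (21) all name times during, at the end of, or after the infusion. The urine footnote (23) names visits only. The default in footnote 1 therefore governs it. The weekly table works the same way.

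**2. Which hours does the urine cover?** Take a 24 h collection that ends at the dose.

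- Schedule 1: dose 1 on Day 1, next dose on Day 22, gap 21 days (Section 3.8). Window = (21 − 1) × 24 to 21 × 24 = 480 to 504 h after dose 1. With the ±3-day dosing window (footnote 24), the outer limits are (20 − 3) × 24 = 408 h and (21 + 3) × 24 = 576 h.
- Schedule 2: last Cycle 1 dose on Day 15, C2D1 on Day 29, gap 14 days. Window = 13 × 24 to 14 × 24 = 312 to 336 h after the Day 15 dose, with outer limits of 288 and 360 h for the ±1-day window. This urine already contains residue from the Day 1 and Day 8 doses.

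Neither window touches 0-24 h.

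**3. How different could the amounts be on Schedule 1?** Assumption: urinary output is proportional to the ADC remaining, which declines mono-exponentially with half-life h days. Then:

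- share of the dose on day 1 = 1 − 0.5^(1/h)
- share between days 20 and 21 = 0.5^(20/h) − 0.5^(21/h)
- ratio of the second to the first = 0.5^(20/h)

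| h (days) | Source | Day 1 share | Day 20-21 share | Ratio |
|---|---|---|---|---|
| 12 | predicted human, Section 3.6.3.1 | 0.056 | 0.0177 | 0.315 |
| 5 | monkey, Section 3.6.3.1 | 0.129 | 0.0081 | 0.062 |
| 4 | monkey, Section 1.2.3.2 | 0.159 | 0.0050 | 0.031 |

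**4. Carry-over in later cycles.** With a dose every 21 days, the pre-dose amount rises relative to C2D1 towards 1/(1 − 0.5^(21/h)). That is 1/(1 − 0.297) = 1.42 at 12 days, 1/(1 − 0.054) = 1.06 at 5 days and 1/(1 − 0.026) = 1.03 at 4 days.

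**5. If a site started collecting at the C2D1 dose instead.** Residue from dose 1 adds 0.5^(21/h) of the dose 2 amount: 0.297 at 12 days, 0.054 at 5 days and 0.026 at 4 days. The urine then covers 0-24 h, but the amount divided by one dose still overstates a single-dose fraction, by about 3% to 30% on this assumption.

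**The case against.** The best reply is that the protocol never says outright that the urine is collected before dosing. That follows from a general default. Section 7.4.2 does not say when the 24 h clock starts. It asks for control urine before dosing, separately from the scheduled aliquot ("approximately 20mL of control is required prior to dosing and a 400mL aliquot"), which can be read as implying that the aliquot is post-dose. It also records actual times and volumes and refers collection details to the Study Procedures Manual, which is not at hand. Section 7 lets the sponsor change PK timings without an amendment. Further, Section 13.7.3.1 speaks of the collection period and does not literally say first dose or first day. Raw urine concentrations are summarised by nominal time range, so the window would be visible there.

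Part of this stands. The pre-dose timing is what the tables require by default, not an explicit instruction for urine, and sites might have done otherwise. It does not rescue Fe. The Screening sample can serve as the control, the default has no stated exception, and the post-dose reading leads to step 5, where carry-over remains. If sites differed, two different quantities would share one name.

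It also stands that the importance is modest. Neither Ae nor Fe is among the PK parameters named for the secondary endpoint, and neither is named as an input to dose escalation, dose selection or stopping.

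**Conclusion.** The point holds. Under the default rule, no scheduled collection covers 0-24 h after a dose, and Fe as computed on Schedule 1 is not the fraction of a dose excreted in the first 24 h. The timing mismatch rests on the tables alone. The ratio of 0.03 to 0.32 rests on the assumption that urinary output tracks the ADC, and on a half-life between 4 and 12 days. It shows direction and rough scale and is not an estimate of bias. The 12-day value is itself a prediction without target.

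Four stronger readings are tempting and not supported:

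- That urinary recovery cannot be obtained at all. An amount in the collected urine can be calculated; what fails is the label and the division by one dose.
- That the gap is three weeks throughout. That is so on Schedule 1, the only schedule with Fe; on Schedule 2 it is two weeks.
- That the toxic moiety's renal handling, and so renal safety, is compromised. Sections 1.2.5.2 and 1.3.1 attribute the renal findings to GSK2857916, not to cys-mcMMAF, and renal safety is followed through creatinine and 24-hour protein and albumin.
- That the trial must add a post-dose collection. The mislabelling can be corrected without one.

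The consequence is limited to a conditional, descriptive Part 1 PK parameter. It should be corrected, but no main conclusion of the trial depends on it.

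**What to change.** In Section 13.7.3.1:

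- rename Ae(0-24) as pre-dose (end-of-interval) 24-hour urinary recovery;
- state the window relative to the previous dose: nominally 480 to 504 h on Schedule 1, and 312 to 336 h after the Day 15 dose on Schedule 2;
- summarise it by cycle as well as by dose and schedule;
- delete Fe.

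This is a wording change and needs no new samples.

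If the sponsor wants a true first-day fraction, a timed 24-hour collection starting at the C1D1 infusion would give one free of carry-over. That is an optional design change. It would cost more than an extra container, because only the sentinel subject has to stay for 24 h (Section 7.3.3) and other subjects might have to collect as outpatients.

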13.7.3.2. Statistical Analysis of Pharmacokinetic Data

Statistical analyses of the pharmacokinetic (PK) parameters data will be the responsibility of Discovery Biometrics, GSK.

GSK2857916 (intact and total) and cys-mcMMAF concentration-time data will be listed for each subject and summarized by descriptive statistics at each time point by cohort.

Dose Proportionality: In Part 1, if more than 2 dose cohorts are required to reach RP2 dose, exploration of dose proportionality for GSK2857916 (intact and total) and Cys-mcMMAF $AUC(0-\infty)/AUC(0-\tau)$ and C_{max} following single dose administration and GSK2857916 (intact and total) and cys-mcMMAF C_{max} and C_{trough} following repeat dose administration will be evaluated graphically and using the power model as described below:

$$\log(\text{pharmacokinetic parameter}) = a + b * \log(\text{dose})$$

where a is the y-intercept and b is the slope.

The power model will be fitted by restricted maximum likelihood (REML) using SAS Proc Mixed. Both the intercept and slope will be fitted as fixed effects. If there is sufficient data, the model may also be fit with the intercept and/or slope as random effects depending on the ability of the model to converge and on estimation of variance-covariance matrix. The mean slope and corresponding 90% confidence interval will be estimated from the power model.

13.7.4. Pharmacokinetic/Pharmacodynamic Analyses

Exploratory plots will be presented to examine potential relationships between individual and/or pooled plasma concentrations/exposure and relevant safety and PD endpoints. If deemed appropriate, further PK/PD modelling will be performed on the safety and PD endpoints selected based on the results of the exploratory graphical analysis showing obvious relationships or trends between the dose, concentration/exposure and the safety and PD endpoints. The choice of the structural PK/PD models will be dependent on the emerging data. More details of any exploratory PK/PD analyses will be provided in the RAP.

The exposure response relationship between GSK2857916 (dose, concentration, C_{max}, or AUC) and clinical activity (e.g. ORR) will also be explored combining Part 1 and Part 2 data together if deemed appropriate.

13.7.4.1. Translational Research Analyses

The results of translational research investigations will be reported either within or separately from the main clinical study report (CSR). All endpoints of interest from all comparisons will be descriptively and/or graphically summarized as appropriate to the data.

Further details on the translational research analyses will be addressed in the Reporting and Analysis Plan (RAP).

13.7.4.2. Novel Biomarker(s) Analyses

The results of these biomarker investigations may be reported separately from the main clinical study report. All endpoints of interest from all comparisons will be descriptively and/or graphically summarized as appropriate to the data.

Additional exploratory analyses may be performed to further characterize the novel biomarker.

13.7.5. Genetic Analyses

Further details on genetic analyses will be addressed in [Appendix 7](#).

13.7.6. Pharmacodynamic Biomarkers and Exploratory Response Prediction Biomarkers

Cell surface BCMA and sBCMA pre dosing will be quantified as a potential predictive biomarker for clinical activity. Post dosing, free surface BCMA and BCMA-drug complex will be quantified to assess proportion of target engagement.

Measurements of sBCMA will include separate assays for free sBCMA and sBCMA complexed with drug.

Post dose measurements of free and complexed BCMA will be used in conjunction with PK data to understand drug/ target interaction during dosing.

If the data permit, an attempt will be made to identify a statistically and clinically meaningful threshold for BCMA expression which serves as an indicator for potential efficacy. Full details of analysis approaches will be provided in the RAP.

13.7.6.1. Exploratory analyses of DNA, and Protein

Exploratory analyses may be performed on remaining study samples for analyses of DNA, RNA and protein to understand changes in response to GSK2857916 treatment.

The results of exploratory investigations will be reported separate from the main clinical study report (CSR). All endpoints of interest from all comparisons will be descriptively and/or graphically summarized as appropriate to the data.

13.7.7. Clinical Activity Analyses

Overall Response Rate (ORR) is one of the secondary endpoints to measure clinical activity of this study.

For multiple myeloma, ORR is defined as the percentage of subjects with a confirmed PR or better (i.e. PR, VGPR, CR and sCR), according to the IMWG Panel I ([Appendix 1](#)), as assessed by the investigator. In addition, Clinical Benefit rate (CBR) is defined as the percentage of subjects with a confirmed MR or better (i.e. MR, PR, VGPR, CR and sCR), according to the IMWG Panel I ([Appendix 1](#)), as assessed by the investigator.

The number and percentage of subjects in the following response categories will be presented sCR (stringent complete response), (complete response) CR, (very good partial response) VGPR, (partial response) PR, (minimal response) MR, stable disease (SD), progressive disease (PD), and not evaluable (NE)

sCR+CR+VGPR+PR for overall response (ORR)

sCR+CR+VGPR+PR+MR for Clinical Benefit rate (CBR)

The corresponding exact 95% CI for ORR and Clinical Benefit Rate (CBR) will also be provided. Subjects with unknown or missing response will be treated as non-responders, i.e., these subjects will be included in the denominator when calculating percentages of response.

For lymphoma, ORR is defined as the percentage of subjects with confirmed CR, or PR, as described in the Revised Response Criteria for Malignant Lymphoma ([Appendix 2](#)). ORR for lymphomas will be summarized in a similar way as multiple myeloma. The corresponding exact 95% CI for ORR will also be provided.

Other exploratory time-to-event (TTE) endpoints related to clinical activity for Part 2 (MM) of this study are TTP, DOR, TTR, and PFS.

Time to disease progression (TTP) is defined as the time from first dose until the earliest date of PD per IMWG, or death due to PD. Determination of dates of TTP event and dates for censoring will be described in the RAP. **Duration of response (DOR)** is defined as the time from first documented evidence of PR or better until disease progression (PD) per IMWG, or death due to PD among subjects who achieve a response

(i.e. confirmed PR or better). Responders without disease progression will be censored at the censoring time point for TTP.

Time to response (TTR) is defined as the time between the date of first dose and the first documented evidence of response (PR or better). Subjects without confirmed response (PR or better) will be censored at the censoring date for TTP.

Progression-free survival (PFS) is defined as the time from first dose until the earliest date of disease progression (PD) per IMWG, or death due to any cause. Determination of dates of PFS event and dates for censoring will be described in the RAP.

For all the TTE endpoints described above, median TTE with 95% CI will be estimated employing the Kaplan-Meier method as data permits. A Kaplan-Meier survival curve will be generated. The number and percentage of subjects who had the event or were censored will also be reported.

Exploratory subgroup analyses may be performed for all endpoints to measure clinical activity as appropriate.

Overall Survival: The protocol is amended to collect long-term survival data (i.e. up to 1 year after last subject completes or discontinues treatment). Subjects who have already completed the study will be contacted to request re-consent.

If all the patients (who were alive at the time of study completion) can be re-consented, OS landmark analysis may be performed at 9 and 12 months using Kaplan-Meier analysis as data permits.

Otherwise, only descriptive analysis (number and % of deaths and lost to follow-up) will be performed.

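### Section 13.7.7 applies Kaplan-Meier to time to response and censors non-responders who can no longer respond, so the curve overstates response; the overall-survival rule is also all-or-nothing.

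*Protocol*

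**What the plan says.** All of this is in Protocol Section 13.7.7 unless another section is named.

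**Time to response**
- The endpoint list: "Other exploratory time-to-event (TTE) endpoints related to clinical activity for Part 2 (MM) of this study are TTP, DOR, TTR, and PFS".
- TTR "is defined as the time between the date of first dose and the first documented evidence of response (PR or better").
- Non-responders: "Subjects without confirmed response (PR or better) will be censored at the censoring date for TTP".
- TTP "is defined as the time from first dose until the earliest date of PD per IMWG, or death due to PD". Its dates are deferred: "Determination of dates of TTP event and dates for censoring will be described in the RAP".
- Estimator for every endpoint on the list: "median TTE with 95% CI will be estimated employing the Kaplan-Meier method as data permits", with a curve and the number and percentage with the event or censored.
- Section 13.7.1 uses the All Treated Population for anti-cancer activity, so non-responders are in the TTR risk set.
- Section 6.3 ends treatment at progression and does not allow retreatment after permanent discontinuation.

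**Overall survival**
- The condition for Kaplan-Meier, with landmarks of 9 and 12 months: "If all the patients (who were alive at the time of study completion) can be re-consented, OS landmark analysis may be performed".
- If that condition is not met: "Otherwise, only descriptive analysis (number and % of deaths and lost to follow-up) will be performed".
- Follow-up runs to one year after the last subject finishes treatment. Section 6.6 also records survival at 3 months after the last dose.

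**The concern.** Kaplan-Meier assumes that a censored subject would go on to have the event at the same rate as those still at risk. For TTR that fails for a non-responder who has progressed or died, because response on study treatment is no longer possible. These are competing events, not independent censoring.

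The rule also supplies no date for its main group. A progressing non-responder has a TTP event, so the TTP censoring date does not exist for that subject. A non-responder who dies of another cause has no TTP event. That subject does have a TTP censoring date, and is censored for TTR although response has become impossible.

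At stake is a TTR curve and median that contradict the ORR in the same report.

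The survival rule is a separate, smaller matter. Incomplete follow-up is the situation in which a time-to-event estimate is needed, yet one missing re-consent removes it.

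**Working it through.** The protocol states no figure for TTR or survival, so there is none to reproduce. The design figures in Section 13.2.2 rest on response counts and are not affected.

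**TTR: inputs**
- True ORR r = 40%, the design alternative in Section 13.2.2; 20%, the null rate, as a second case.
- Horizon 48 weeks, the 16-cycle treatment period of Section 3.3.1.1 (48 × 7 / 30.44 = 11.04 months).
- Median time to progression without response: 3, 6 or 12 months. This is an assumption; the protocol gives none.
- Response timing: constant hazard throughout, or only in the first 6 or first 3 months. Also an assumption.

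**TTR: formulas.** Let a be the response hazard during a response window of length w, and b = ln 2 / (median time to progression).
- True cumulative incidence: a/(a+b) × (1 − exp(−(a+b)w)). Choose a so that this equals r.
- What Kaplan-Meier estimates with progressors censored at progression: 1-KM = 1 − exp(−a·w).

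Example with r = 40%, median 6 months and w = 11.04: b = 0.1155 and a = 0.0925. Cumulative incidence is 0.0925/0.2080 × (1 − exp(−2.297)) = 0.40. 1-KM is 1 − exp(−1.022) = 0.64, with an apparent median of ln 2 / 0.0925 = 7.5 months.

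**1-KM at 48 weeks when the true ORR is 40%**

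| Responses occur | Median to progression 3 mo | 6 mo | 12 mo |
|---|---|---|---|
| throughout | 82% | 64% | 52% |
| first 6 months only | 66% | 53% | 47% |
| first 3 months only | 53% | 47% | 43% |

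With responses throughout, the apparent medians are 4.4, 7.5 and 10.4 months, although only 40% ever respond. A median is shown wherever the entry exceeds 50%: six of the nine cells. For a true ORR of 20% the same grid runs from 22% to 49%.

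**A second parametrisation.** Set the median time to the first of response or progression at 2 to 3 months, with total hazard h = ln 2 / median and response hazard 0.4h. At 12 months, 1-KM = 1 − exp(−0.4 × h × 12):
- Median 3: h = 0.231, so 1-KM = 67%; true incidence 0.4 × (1 − 1/16) = 38%.
- Median 2: h = 0.347, so 1-KM = 81%; true incidence 0.4 × (1 − 1/64) = 39%.

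The apparent medians, ln 2 / (0.4h), are 7.5 and 5.0 months.

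**Survival: how often the condition is met.** If each of m survivors independently re-consents with probability q (assumed), all do so with probability q^m:
- q = 0.90: 35% for m = 10, 21% for m = 15, 12% for m = 20.
- m = 20: 36% at q = 0.95, 67% at q = 0.98.

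**Survival: what the fallback shows.** In simulations of 40 subjects with 12-month mortality assumed at 30% or 50% and re-consent of 50–90% unrelated to prognosis:

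| True 12-month mortality | Crude deaths by 12 months | Crude deaths counted to 24 months |
|---|---|---|
| 30% | 24.5–28.8% | 35–48% |
| 50% | 41.5–48.2% | 54–71% |

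The crude percentage lies below 12-month mortality at the first horizon and above it at the second.

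If only subjects still alive at contact can re-consent, Kaplan-Meier with ordinary censoring is itself low: 25–29% for a true 30%, and 44–49% for a true 50%.

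**The case against.** **On TTR.** The reporting and analysis plan (RAP), not shown here, is to define the censoring dates, so the missing date for progressors may be supplied there. That stands as to the date. It does not rescue the estimator, because a TTP-type date at or before progression or death gives the bias shown. Only carrying non-responders forward as non-responders to the end of follow-up would remove it, and that is no longer a TTP censoring date.

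The size depends on response timing: with early responses and slow progression the excess is 3 points and no false median appears. That also stands, and is why the range is wide.

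The consequence is limited. TTR is exploratory. ORR is reported with an exact interval and counts missing responses as non-response. The event count is printed with each curve, and the futility rules use response counts. All of this is correct.

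**On survival.** The rule is partly a sensible caution: follow-up was added by amendment, re-consent requires being alive, and Kaplan-Meier on such data can be biased. The objectives list only the number of deaths, which the fallback gives. That stands as a reason for care, but not for an all-or-nothing switch.

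A reader might infer three stronger things that the documents do not support:
- *The fallback understates mortality.* It has no time horizon, and with longer follow-up it can exceed 12-month mortality.
- *It treats unfollowed subjects as alive.* Loss to follow-up is reported as its own category.
- *It is almost certain to be triggered.* That depends on the number of survivors and the re-consent rate, neither of which is given; the chance that all re-consent ran from 12% to 67% above.

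**Conclusion.** The TTR point holds. As written, the rule censors subjects who cannot respond, leaves the date undefined for those who progressed, and requires a Kaplan-Meier curve and median. In every scenario tried, 1-KM exceeded the true response probability. For a true ORR of 40% it read about 43% to 82%, often with a median that does not exist among all treated subjects. The direction follows from censoring at or before a competing event; the size rests on assumed hazards and response timing. The error is confined to an exploratory endpoint. ORR, the futility looks and the design's operating characteristics are unaffected.

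The survival point is secondary and narrower. Kaplan-Meier is dropped if a single survivor is not re-consented, and its replacement is a percentage that cannot be interpreted in time, with a direction of error that depends on follow-up.

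**What to change.** **TTR.** Remove it from the Kaplan-Meier list. Either summarise median and range in confirmed responders only, or give the cumulative incidence of response in all Part 2 MM subjects with progression and death as competing events. Replace the reference to the TTP censoring date accordingly.

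**Overall survival, if reported.** Drop the condition that every survivor re-consent. Give Kaplan-Meier at 9 and 12 months, with subjects not re-consented censored at last known alive date; the 3-month status in Section 6.6 provides one. Let re-consented subjects re-enter the risk set at re-consent, so that the gap before contact is not counted as guaranteed survival. State the number re-consented, and add a sensitivity analysis for re-consent that depends on prognosis.

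**Cost.** Analysis wording and a few lines of programming. No new data, visits or subjects.
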